2. Inclusion and Exclusion Criteria

- i. Inclusion criteria: All spontaneously breathing subjects, 18 years of age and older, with an American Society of Anesthesiologists (ASA) Physical Status Classification 1 or 2, who will be receiving sedation for an ED procedure.

Written informed consent will be obtained from all subjects.

- ii. Exclusion criteria: Subjects with underlying conditions that could affect ventilation, perfusion, or metabolism including intubated subjects, subjects with clinical signs of cardiopulmonary instability, major trauma, shock, sepsis, ASA class 3, 4, and 5. Also those unable to provide informed consent, nursing home residents, age less than 18 years, non English speaking, pregnant women, subjects under police custody, or physician discretion.

3. Study Endpoints

- i. Primary:

1. ETCO₂ measured q 20 milliseconds seconds
2. SpO₂ measured q 20 milliseconds seconds

- ii. Secondary Endpoints

1. A baseline reading of the vital signs (heart rate, respiratory rate, peripheral SaO₂ and ETCO₂)
2. Physician interventions (verbal or physical stimulation, airway repositioning, additional oxygen, positive pressure ventilation, endotracheal intubation)
3. Level of sedation (Ramsay Score)
4. Patient Demographics
5. Patient recall of procedure
6. Total propofol dose
7. Total elapsed time of nitrous oxide use
8. Patient and physician procedure satisfaction score

4. Procedures Involved in the Research

Initial medical assessment will be made in accordance with established clinical procedures, including the history, physical examination, and vital signs. If by clinical assessment the patient meets eligibility criteria, then they will be approached by a research associate for enrollment in the study. After informed consent is obtained and prior to starting the sedation, standard vital sign monitoring will be placed on the patient (electrocardiogram, non-invasive blood pressure monitoring, pulse oximetry, and capnography). Level of consciousness will be determined using the modified Ramsay scale, which will be assessed at baseline. The Capnostream 20 ETCO₂ monitor will be used as the primary device to measure ETCO₂, with a nasal cannula capable of delivering supplemental oxygen and measuring ETCO₂ (Oridion Medical, Needham, MA).

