Vital signs will be flagged electronically when a physician intervenes for clinical respiratory depression. Respiratory depression will be defined as peripheral SaO₂ below 92%, ETCO₂ level above 50, a rise or decrease of 10% above or below baseline, the loss of the ETCO₂ waveform for more than 15 seconds. Level of consciousness will be determined using the modified Ramsay scale, which will be recorded at baseline and at the point of deepest sedation. Once the procedure is complete, and the patient is deemed back to their mental status baseline, they will fill out a post procedure satisfaction questionnaire, and a 100mm VAS scale. They will be asked about procedure recall. The physician will also fill out a post procedure questionnaire.

5. Data Management

A standardized data collection form will be used to collect clinical data and a USB drive to collect electronic vital sign data. Initial data gathered will include age, gender, weight, and baseline vital signs (BP, HR, RR, peripheral SpO₂, and ETCO₂). Other information collected will be the elapsed time of nitrous oxide use, start time (when protocol was given), time (when patient returns to baseline), elapsed time in seconds under sedation (from start time to end time),

medications administered, repeated doses and times for every administered medication, total dose of each medication administered, adverse events, and interventions aimed at correcting respiratory depression. Level of consciousness using the modified Ramsay scale will also be recorded at baseline and at set intervals during sedation.

The electronic monitoring data will be continuously recorded into the USB drive throughout the sedation and recovery periods. The Capnostream 20 ETCO₂ monitor (Oridian Medical, Needham, MA) is capable of sampling and recording ETCO₂ and pulse SaO₂ every 5 seconds. A patient identifier will be recorded to link the subject and the electronic monitoring data without compromising his/her confidentiality. At the completion of the sedation, all device data will be transmitted to a password-protected Excel/SPSS spreadsheet for analysis. The research associate is responsible for recollection and storage of the data. Only the primary investigators, the study coordinator, and the research associates will have access to such.

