To assess these outcomes, we will download electronic data from each sedation into a Microsoft Excel database, checked and adjudicated any discrepancies with research associate notations, and generate a graph of the subject's sedation with the X-axis showing time and the Y-axis depicting ETCO₂, SpO₂, respiratory rate, and heart rate. Electronic time stamps noted propofol administration, procedure initiation and completion, adverse events, and physician interventions.

Before study blinding is broken, three investigators will evaluate each graph to code the presence or absence of cerebral hypoxia, peripheral hypoxia and respiratory depression. We will disqualify graphs if they had >35% data loss, unless all three evaluators agreed that there was unequivocal evidence of hypoxia (cerebral and or peripheral) and/or respiratory depression.

6. Withdrawal of Subjects

Participation is voluntary. Subjects may withdraw from this study at any time. If this is the case their data will be deleted. We will record the number of patients that withdraw. Subjects may be withdrawn without their consent if the electronic data cannot be recorded.

Statistical Plan

1. Sample Size Determination

As this is a pilot, prospective, observational trial, no power calculation will be used to measure a difference. In previous propofol studies, approximately 10-30% of patients develop hypoxia, and approximately 50% of patients meet criteria for respiratory depression. Thus, we believe enrolling 100 patients in this observational trial will allow for approximation of any correlations that are measured.

2. Statistical Methods

All clinical observations and demographic data will be summarized using medians with range or means with standard deviations as appropriate. Rate of detection of respiratory depression and hypoxia and timing of these events for each instrument (near-infrared spectroscopy, pulse oximetry, capnography) will be summarized descriptively. Associations among SaO₂, and ETCO₂ will be estimated using spearman's rank correlation coefficient, using within-cluster resampling algorithm. This will allow for estimation of the marginal correlation in the presence of clustered data. Correlations not involving repeated measures data will be estimated with Spearman's rank correlation coefficient. All analysis will be conducted using SPSS software (IBM, Armonk, NY).

Risks to Subjects

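### Events with numeric limits are to be coded by eye from graphs, with no programmed check and no stated masking of intervention and adverse-event time stamps

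*Combined protocol and SAP*

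**What the plan says.** Specific Aims targets the rates of hypoxia and of respiratory depression that needed a physician to intervene. Study Design section 3 makes the primary endpoints device readings of ETCO₂ and SpO₂.

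Section 4 gives the limits: "Respiratory depression will be defined as peripheral SaO₂ below 92%, ETCO₂ level above 50, a rise or decrease of 10% above or below baseline", or loss of the ETCO₂ "waveform for more than 15 seconds". It adds: "Vital signs will be flagged electronically when a physician intervenes for clinical respiratory depression".

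Section 5 sends the device data to an Excel/SPSS spreadsheet and has one graph drawn per subject, with time on the X-axis and "the Y-axis depicting ETCO₂, SpO₂, respiratory rate, and heart rate". The next sentence reads: "Electronic time stamps noted propofol administration, procedure initiation and completion, adverse events, and physician interventions". Then "three investigators will evaluate each graph to code the presence or absence of cerebral hypoxia, peripheral hypoxia and respiratory depression". Graphs with more than 35% data loss are dropped unless all three readers agree that an event is unequivocal. The plan has no other rule for disagreement, no agreement statistic, no programmed comparison with the limits, and no statement that the time stamps are concealed from the readers.

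**The concern.** When an outcome is a number crossing a limit and the numbers are stored, visual coding adds reader error that the data do not require. Two readers can differ on whether a trace dipped just under 92%; a program cannot.

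The more serious issue is independence. The main aim joins two facts about each subject: that an event occurred and that a physician intervened. If the reader can see the intervention mark while deciding whether there was an event, the second fact informs the first. A marked subject who crossed no limit may be coded as an event, and each such call where the mark is an intervention goes straight into the rate that the study sets out to measure. With no comparison group described, the error cannot cancel between arms. It falls on the absolute rates and on any informal comparison with the earlier propofol figures under Sample Size Determination (hypoxia 10-30%, respiratory depression about 50%).

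**Working it through.** The plan states no reader error rate, agreement figure or precision target, so there is nothing of its own to reproduce. The check has three parts.

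**1. What can be programmed as written**

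| Item to be coded | What the plan gives | Programmable now? |
|---|---|---|
| SaO₂ limb | below 92% | Yes |
| ETCO₂ limb | above 50 | Yes |
| 10% change from baseline | variable not named | No |
| Waveform loss | over 15 s | Only by approximation from stored readings |
| Peripheral hypoxia | no threshold of its own | No |
| Cerebral hypoxia | no threshold; section 4 names no near-infrared device | No |

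The waveform limb also depends on the sampling interval, which conflicts. Section 3 has "SpO₂ measured q 20 milliseconds seconds"; section 5 says the monitor records every 5 seconds. Fifteen seconds is 15/5 = 3 readings on one statement and 15/0.02 = 750 on the other.

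**2. Whether the readers see the marks**

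Section 5 lists the plotted quantities, then the time stamps in the next sentence, then the reading task. Section 4 puts an intervention flag on the vital-sign record itself. The natural reading is that the marks appear on what the readers see, but no sentence says so. Section 5 does say that coding precedes the breaking of study blinding. In a non-randomized study with no comparator described, that phrase has no clear meaning, and treatment blinding would not conceal intervention marks.

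**3. How large the effect could be (illustration; reader behaviour is assumed)**

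Inputs from the plan: n = 100 and expected rates p of 10%, 30% and 50%.

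*Sampling error*, 1.96 × √(p(1−p)/100): 5.9, 9.0 and 9.8 points. Exact 95% intervals are 4.9-17.6%, 21.2-40.0% and 39.8-60.2%.

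*Visible marks.* Let q be the share of true non-events carrying a mark and f the share of those wrongly coded as events. The upward shift is (1−p) × q × f. With q from 10% to 30% and f from 10% to 50%:

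- p = 10%: 0.9 × 0.1 × 0.1 = 0.9 points, to 0.9 × 0.3 × 0.5 = 13.5 points
- p = 30%: 0.7 to 10.5 points
- p = 50%: 0.5 to 7.5 points

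The upper end exceeds the sampling half-width at 10% and 30% and is below it at 50%. The lower end is negligible.

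*Reader error without marks.* Apparent rate = p × Se + (1−p)(1−Sp). With Se = Sp = 0.90, a true 10% reads as 0.09 + 0.09 = 18%, 30% as 34% and 50% as 50%. With Se = Sp = 0.95, 10% reads as 14% and 30% as 32%.

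*Unstated rule for combining readers.* For three independent readers with Se = Sp = 0.90 and a true 30%:

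- any reader: 0.3 × 0.999 + 0.7 × 0.271 = 48.9%
- majority: 0.3 × 0.972 + 0.7 × 0.028 = 31.1%
- all three: 0.3 × 0.729 + 0.7 × 0.001 = 21.9%

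**The case against.** The strongest reply has four parts.

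- **Display is inferred.** The plan does not say that the marks are drawn on the graph. This stands, so the bias argument has to be conditional. Nothing in the plan promises concealment either.
- **A program cannot replace the readers as things are.** Only the SaO₂ and ETCO₂ limits can be coded as written. This also stands. The gaps have to be closed under either method, because readers without a definition of cerebral hypoxia are no better placed than a program.
- **Automation has its own error.** The SaO₂, ETCO₂ and 10% limbs have no minimum duration, so a program would count one stray reading from a loose probe or cannula. This is fair. It calls for artefact rules written beforehand and is the reason to keep human review for that purpose.
- **Safeguards exist and the stakes are modest.** There are three readers, discrepancies are checked against the research associate's notes, and this is a descriptive pilot. Three readers reduce random error only once a combining rule is stated, and they do not remove a cue that all three can see. The descriptive purpose keeps this a recommended improvement rather than a flaw that would stop the study.

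A reader might infer that drawing four signals on one axis makes small crossings unreadable. The documents do not give the axis scale, and values can be looked up in the spreadsheet, so this is not shown.

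**Conclusion.** The point holds in a limited form. The plan has numeric limits and stored data, codes by eye without a programmed check, and does not say that intervention and adverse-event marks are hidden. If they are visible, event and intervention are not assessed independently, and the rate in Specific Aims can be biased. The size is not calculable from the documents: every figure that depends on q, f, Se or Sp rests on assumed reader behaviour, and the shifts from visible marks run from under 1 point to more than the sampling error at n = 100.

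Three stronger conclusions are tempting and not supported: that the readers certainly see the marks, that the published rate will be inflated by a known amount, and that every coded outcome could be programmed today at a saving of investigator time.

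**What to change.** 1. Derive the SaO₂ below 92% and ETCO₂ above 50 events with a prespecified program run on the stored records.
2. Before any coding, have the investigators write down what is missing: the variable for the 10% change, how waveform loss over 15 seconds is read from stored data, and the definitions of peripheral and cerebral hypoxia. Reconcile the 20-millisecond and 5-second sampling statements. Then program these parts too.
3. Use the three readers only to judge artefact and data loss, on traces with intervention and adverse-event marks hidden, with the majority deciding. The exception for graphs above 35% loss now depends on readers calling an event, so it must be reworded to fit.
4. Link the intervention time stamps to the derived events afterwards. The main aim is still served, because the stamps are kept and only their timing in the process changes.

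The cost is a short program and some definitional work, with no change to enrolment, treatment or data collection. The artefact rules must be fixed in advance, since otherwise single out-of-range readings could count as events. The readers still have to view the traces, so the gain is reproducibility and independence, not time. The sample size is unaffected.

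### A graph with more than 35% data loss re-enters the rates only through an agreed event, and the plan reports neither how many such graphs there are nor how far they move the rates

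*Combined protocol and SAP*

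**What the plan says.** Section 5, Data Management, has three investigators code each subject's graph for the presence or absence of hypoxia and respiratory depression. It then sets a quality rule: "We will disqualify graphs if they had >35% data loss, unless all three evaluators agreed that there was unequivocal evidence of hypoxia". The exception in full covers "unequivocal evidence of hypoxia (cerebral and or peripheral) and/or respiratory depression". There is no matching exception for a poor graph that the evaluators agree shows no event.

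The same section says that the electronic data are "checked and adjudicated any discrepancies with research associate notations". It does not say that this step restores or codes a disqualified graph. It also says: "Electronic time stamps noted propofol administration, procedure initiation and completion, adverse events, and physician interventions".

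Statistical Plan, 2. Statistical Methods, promises a descriptive summary of the "Rate of detection of respiratory depression and hypoxia and timing of these events for each instrument". No denominator is given. Section 6, Withdrawal of Subjects, adds "Subjects may be withdrawn without their consent if the electronic data cannot be recorded" and "We will record the number of patients that withdraw". That is a separate route out of the study, and its count is not tied to these rates.

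Section 4, Procedures, makes loss of the ETCO2 waveform beyond 15 seconds one of the criteria for respiratory depression. The plan does not say whether such loss also counts toward the 35%.

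**The concern.** For a poor graph the only way back into the analysis is an agreed event. A graph with no agreed event of either kind is removed. Selection on the outcome is therefore built into the rule and occurs when the rule is followed exactly.

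There is one partial exception. A graph rescued for respiratory depression alone may enter the hypoxia rate as non-hypoxic, although much of its trace is missing.

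Signal loss and the outcome may also be linked, because a lost waveform can itself be the event. The size and sign of the error then depend on quantities that the plan does not report.

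The study is a single-arm description of safety. The absolute rates are the result, and there is no comparator in which the error could cancel. Selection bias does not shrink with sample size, and a confidence interval does not show it.

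**Working it through.** The plan has no figure of its own to reproduce: the 100 subjects are not derived from a power or precision calculation.

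**Inputs from the plan.** N = 100 (Study Design). Expected rates come from 1. Sample Size Determination: "approximately 10-30% of patients develop hypoxia, and approximately 50% of patients meet criteria for respiratory depression".

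**Inputs assumed (not in the plan).**
- f: share of graphs with more than 35% loss
- s: chance that an event in a poor graph is agreed by all three evaluators
- v: share of event-free poor graphs wrongly agreed as events (0 unless stated)
- pg and pb: true event rates in good and poor graphs

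Disqualified graphs are taken to leave the denominator. This is the natural reading, but it is not stated.

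**Formula.** Reported rate = [pg(1−f) + pb·f·s + (1−pb)·f·v] / [(1−f) + pb·f·s + (1−pb)·f·v]

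**1. Loss unrelated to events, true respiratory-depression rate 50%.**

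| f | s = 0.25 | s = 0.5 | s = 0.8 | s = 1 |
|---|---|---|---|---|
| 10% | 50.7% | 51.4% | 52.1% | 52.6% |
| 20% | 51.5% | 52.9% | 54.5% | 55.6% |

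Example, f = 20%, s = 0.8: (40 + 8)/(80 + 8) = 48/88 = 54.5%. At f = 5%, s = 1: 50/97.5 = 51.3%, a shift of 1.3 points. The 95% half-width at N = 100 is 1.96·√(0.5·0.5/100) = 9.8 points.

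**2. Loss linked to events (50% in good graphs, 75% in poor ones).** Errors in percentage points:

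| f | True rate | s = 0.25 | s = 0.5 | s = 0.8 | s = 1 | Drop all poor graphs |
|---|---|---|---|---|---|---|
| 10% | 52.5% | −1.5 | −0.5 | +0.6 | +1.3 | −2.5 |
| 20% | 55.0% | −2.8 | −0.7 | +1.5 | +2.9 | −5.0 |

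Example, f = 20%, s = 0.8: (40 + 12)/(80 + 12) = 52/92 = 56.5%, against 55.0%. The sign changes at s = 0.59 (f = 20%) and s = 0.63 (f = 10%). At f = 20% the existing rule is closer to the truth than outcome-blind exclusion once the poor-graph rate exceeds 54%, 59%, 64% or 68% (s = 0.25, 0.5, 0.8, 1).

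**3. Bounds for respiratory depression (N = 100, f = 20%, s = 0.8).** Agreed events stay events. The remaining poor graphs count first as non-events, then as events.
- True 50%: lower 40 + 8 = 48%, upper 40 + 20 = 60%.
- True 55%: lower 40 + 12 = 52%, upper 60%.
- With false agreement the lower bounds become 48 + 10v and 52 + 5v. They pass the truth at v > 0.2 and v > 0.6. A lower bound that does not rely on the agreed calls is 40%.

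**4. Hypoxia (rate h, treated as a subset of respiratory depression at 50%; f = 20%).** Reported rate = (80h + 20h·sh)/(80 + 10·sr), where sh and sr are the recognition chances for hypoxia and respiratory depression.
- sh = sr = 0.8: 9.6/88 = 10.9%, 19.2/88 = 21.8% and 28.8/88 = 32.7% for true 10%, 20% and 30%.
- Bounds 80h + 16h to 80h + 20: 9.6-28.0%, 19.2-36.0% and 28.8-44.0%. At 20% the lower bound is 19.2 + 16v and passes the truth at v > 0.05.
- sh = 0.3, sr = 0.8, true 20%: 17.2/88 = 19.5%. The error is now downward, because rescued graphs enter as non-hypoxic.

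**5. Withdrawals.** Suppose 5 of 100 sedated subjects are withdrawn for unrecordable data. The 95 retained are 76 good graphs (38 events) and 19 poor ones (9.5 × 0.8 = 7.6 agreed). The bounds are 45.6/95 = 48% to 57/95 = 60%. Over all 100 they are 45.6% to (57 + 5)/100 = 62.0%.

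**The case against.** The strongest defence is that the rule has a measurement rationale. A partial trace can prove that an event occurred, but it cannot prove that none did. Requiring unanimity and clear evidence also limits false rescues. In scenario 2 the rule is nearer the truth than outcome-blind exclusion at every s shown. This stands, and it is why the exception should not simply be deleted. It does not provide a route back for event-free graphs, and it does not tell a reader how many graphs were rescued.

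The other objections stand in part:
- **Size.** It rests on assumed f, s, v and poor-graph rates. Nothing in the plan makes 20% poor graphs more likely than 5%, where the shift is at most 1.3 points.
- **Direction.** It depends on the unstated denominator. If disqualified graphs stayed in as non-events, the main example would give 48/100 = 48% against a true 50%, an underestimate.
- **Link to the reported rates.** The Statistical Methods section speaks of rates per instrument and does not say outright that these use the investigators' codes. The link is inferred from the Data Management text, which introduces the graphs as the means of assessing the outcomes.
- **Aim.** Specific Aims can be read as confining both outcomes to events that needed a physician's intervention. Interventions are recorded on the data form and time-stamped, so that rate need not be affected. If the qualifier applies to respiratory depression only, the hypoxia rate remains exposed.

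**Conclusion.** The concern holds. Inclusion of a high-loss graph depends on the outcome, and the plan offers nothing from which a reader could judge the effect.

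With disqualified graphs out of the denominator, loss unrelated to events and no false agreements, the respiratory-depression rate is inflated: by 0.7 to 2.6 points at 10% poor graphs and 1.5 to 5.6 points at 20%, for a true rate of 50%. If loss goes with events, the error can take either sign. Neither the rate with the rescued graphs nor the rate without them can then be called unbiased.

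The consequence is limited. This is a single-arm descriptive pilot, the shifts shown are below the sampling half-width, and the physician-intervention rate need not be touched. It is a point that should be fixed, not one that undermines the study.

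**What to change.** Do not report the rate under the exception alone. For hypoxia and respiratory depression separately:

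1. Report the number of graphs with more than 35% loss, the number rescued and the number disqualified. Alongside, give the number of subjects withdrawn because electronic data could not be recorded.
2. Report each rate with and without the rescued graphs, each with its denominator, and present neither as unbiased.
3. Give bounds over all sedated subjects with retained data. Agreed events in high-loss graphs stay events; the other high-loss subjects count first as non-events, then as events. State that the lower bound assumes the unanimous calls are correct. If subjects were withdrawn for unrecordable data, show the bounds again with them added in the same two ways; only their number is needed.
4. State how data loss is computed for SpO2 and ETCO2, and whether waveform loss that meets the respiratory-depression criterion in section 4 counts toward the 35%.

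Compute the physician-intervention rate on all sedated subjects with retained data, from the data form and the time stamps.

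The cost is a few sentences and table rows. No new data are needed, and no graph that the current rule keeps is lost. The price is a wider stated range: at f = 20%, s = 0.8 and a true rate of 50%, the report would show 48/88 (54.5%), 40/80 (50.0%) and bounds of 48-60% in place of one figure.
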